8.1 EFFICACY ENDPOINTS

The primary efficacy endpoint of this trial is change in corrected distance visual acuity (CDVA) at the last required study visit (6 months post-op), compared to baseline. CDVA will be evaluated by an observer who is masked to the treatment protocol to which study subjects have been assigned. All eyes treated (single or both eyes of an individual subject) will be included in the analysis of efficacy.

The Secondary Endpoints will be:

1. Change in UCVA at 6 months, compared to baseline.
2. Change in K_{\max} , compared to baseline.

Additional analyses will be performed in subgroups of patients using standard statistical stratification methods, including patients over the age of 35, patients under the age of 18, disease severity, and patients with and without pre-procedure corneal scars. Results in male vs. female patients and post LASIK ectasia vs. primary keratoconus will also be evaluated.

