3.0 STUDY DESIGN

3.1 OBJECTIVE

The objective of this study is to assess changes in visual acuity after corneal collagen cross-linking of asymmetric corneas.

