3.4 STUDY POPULATION

Up to 3,000 subjects with asymmetric corneas will be enrolled. After providing informed consent and documenting it in writing, subjects with keratoconus, forme fruste keratoconus, post-LASIK ectasia, pellucid marginal degeneration, forme fruste pellucid marginal degeneration, diurnal fluctuation after RK, or Terrien's marginal degeneration will be screened for participation in the study. Screening evaluations may be performed at any time within 3 months preceding or on Day 0, and subjects must fulfill the following criteria:

Inclusion Criteria:

1. Diagnosis of keratoconus, forme fruste keratoconus, post-LASIK ectasia, pellucid marginal degeneration, forme fruste pellucid marginal degeneration, history of radial keratotomy with fluctuating vision, or Terrien's marginal degeneration.
2. Must have provided informed consent, documented it in writing, and have been given a copy of the signed informed consent form.
3. Must be willing and able to return for scheduled treatment and follow-up examinations for the duration of the study.
4. Must be at least 8 years of age.

Exclusion Criteria:

1. Corneal thickness < 375 microns measured by ultrasound or Pentacam.
2. Contraindications or sensitivities to any study medications or their components.
3. Pregnancy or breastfeeding.
4. Any history of herpes simplex corneal disease in an eye to be treated.
5. Nystagmus or any other condition that would, in the judgement of the investigator, prevent a steady gaze during the treatment.
6. Inability to cooperate with diagnostic tests.
7. Enrollment in another ophthalmic clinical trial.

Randomization:

Randomization will be stratified by indication and by investigational site, with study subjects randomly assigned to one of three treatment groups. The three treatment groups consist of CXLO Corneal Strengthening Solution combined with one of 3 different UVA exposure parameters. The UVA treatment parameters will consist of:

- Group 1: 4 mW/cm² cycled On/Off automatically at 15 second intervals for 20 minutes (total UVA corneal surface dose of 2.4 J/cm²),
- Group 2: 6 mW/cm² cycled On/Off automatically at 15 second intervals for 20 minutes (total UVA corneal surface dose of 3.6 J/cm²), and
- Group 3: 4 mW/cm² cycled On/Off automatically at 15 second intervals for 30 minutes (total UVA corneal surface dose of 3.6 J/cm²).

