8.0 STATISTICAL PLAN

Change from baseline will be calculated as follow-up visit – baseline. The baseline visit will be defined as Visit 1 (Pre-procedure visit). The required analyses and target endpoints include, but are not limited to those listed below. In general, continuous variables will be analyzed with two-sample t-tests for changes from baseline in normally distributed variables. For non-parametric data sets, Wilcoxon Signed Rank tests will be utilized. Patient demographics will be summarized using descriptive statistics (means, medians, standard deviations, etc.).

Subject demographic characteristics and background variables will be summarized. Treatment differences with respect to baseline characteristics will be discussed in the final study report and assessed.

All subjects enrolled in the study will be included as part of the safety analysis. All eyes treated (single or both eyes of an individual subject) will be included in the analysis of safety and efficacy.

To determine efficacy, standard statistical methods such as p value analyses of continuous variables will be used along with newer artificial intelligence algorithms such as *Logitboost* or *Random Forest* to detect groupings and correlations of various outcome variables.¹ Large data sets will be analyzed and in these analyses stratification by age, diagnosis, severity of disease, gender, tomography, topography metrics and other such criteria will be used to answer key questions related to the science and effects of treatments.

Reference: ¹*Statistical Learning for Biomedical Data* JD Malley, KG Malley, S Pajevic Cambridge University Press, 2011).

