1.6 Changes from Protocol

The protocol states the primary efficacy endpoint of this trial is change in corrected distance visual acuity (CDVA) at the last required study visit (6 months post-op), compared to baseline. For this analysis, the change in CDVA will be estimated at Month 6 as well as Month 12.

The protocol also states that two-sample t-tests will be used for treatment comparisons. Since there are three treatment groups, analysis of variance (ANOVA) will be used instead of conducting separate t-tests on each pairwise combination of treatments. Separate t-tests on each pairwise comparison will be performed as a supportive analysis.

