5.1 Primary Efficacy Endpoint

The primary measure of efficacy is the mean change from baseline in LogMAR of Corrected Distance Visual Acuity (CDVA) in the Primary Eye at Month 12 for each treatment group. As supportive analysis to the primary endpoint, the mean change from baseline and treatment differences will be estimated at Month 3 and Month 6.

Separately for each timepoint, analysis of variance (ANOVA) will be used to obtain point estimates and CIs for the change from baseline in LogMAR CDVA for each group. ANOVA will also be used to obtain point estimates and CIs for all pairwise comparisons between the treatment arms. P-values may be provided for descriptive purposes only.

As a sensitivity analysis, separate point estimates and confidence intervals for treatment differences based on a two-sample t-tests for each pairwise comparison will be performed without assuming equal variances. Satterthwaite approximation for degrees of freedom will be used.

Other sensitivity analysis such as mixed models repeated measures to account for the longitudinal nature of the data may be considered in an ad hoc manner.

The primary analysis will be repeated for the Fellow eye.

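### The protocol does not say which comparison among its three active arms decides the 6-month CDVA primary endpoint, and the tests it names answer different questions

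*Protocol*

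**What the plan says.** **Protocol.** Section 3.1 states the aim without a comparison: "The objective of this study is to assess changes in visual acuity after corneal collagen cross-linking of asymmetric corneas". Section 3.4 has "study subjects randomly assigned to one of three treatment groups", and "The three treatment groups consist of CXLO Corneal Strengthening Solution combined with one of 3 different UVA exposure parameters", so every arm is active. Section 8.1 sets the primary endpoint as "change in corrected distance visual acuity (CDVA) at the last required study visit (6 months post-op), compared to baseline".

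For testing, section 8.0 states that "continuous variables will be analyzed with two-sample t-tests for changes from baseline in normally distributed variables", and then that "For non-parametric data sets, Wilcoxon Signed Rank tests will be utilized". The same section says p-value analyses will be used in determining efficacy. No arm, contrast, null hypothesis, alpha or success rule is attached to the primary endpoint in 8.0, 8.1, 8.2 or the summary.

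**SAP.** Section 1.6 reads the protocol's t-tests as treatment comparisons and substitutes ANOVA because there are three groups, adding: "Separate t-tests on each pairwise comparison will be performed as a supportive analysis". Section 5.1 makes the primary measure each group's mean change at Month 12, with Months 3 and 6 supportive. It continues: "ANOVA will also be used to obtain point estimates and CIs for all pairwise comparisons between the treatment arms". No overall three-group test is mentioned. Section 3.5 rules out multiplicity adjustment. Section 3.2.3.1 says the efficacy analysis tests no hypotheses and its estimates are descriptive. The Introduction limits this SAP version to the analyses supporting an FDA meeting.

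**The concern.** A two-sample t-test of change compares two groups. With three groups there are three such comparisons, and the protocol does not name or rank them. The signed-rank test asks whether change within one group is centred on zero. Read literally, the shape of the data would therefore decide whether the primary analysis compares regimens or compares follow-up with baseline.

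Randomisation can answer whether the three UVA regimens differ, and no test is designated for that question. Unranked pairwise tests give three chances of a false claim that one regimen is better. Before-after tests have no untreated arm to separate a treatment effect from practice, better refraction or any other shift shared by all arms.

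**Working it through.** **What can be reproduced.** The only design figure is 3,000 subjects (Protocol 8.2). It comes without alpha, power, effect size, SD or a named comparison, so it cannot be reproduced.

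**Assumptions.** Two-sided 5% per test (the protocol states no alpha; the SAP uses 95% intervals), equal allocation giving 1,000 per arm, and one eye per subject unless stated. The SD of CDVA change is taken over 0.10 to 0.25 logMAR.

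**1. What 1,000 per arm buys depends on the unnamed comparison.** Detectable effect at 80% power:
- One named between-arm contrast: √(2/1000) × (1.960 + 0.842) = 0.125 SD.
- Three pairs, Bonferroni at 0.0167 each: 0.145 SD.
- A within-arm change: √(1/1000) × 2.802 = 0.089 SD.

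**2. Three unadjusted pairwise tests.** With no true difference, the chance of at least one |z| > 1.96 is the upper tail of the studentised range for three groups at 1.96 × √2 = 2.772. This is 0.122, or 2.4 times 5%.

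**3. Before-after tests with a common shift.** Suppose every arm improves by 0.02 logMAR (one letter, at five letters per 0.1) and the regimens do not differ. Power in each arm is Φ(0.02 / (SD/√1000) − 1.96).

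| SD of change | z | Power in each arm |
|---|---|---|
| 0.10 | 6.32 | >0.999 |
| 0.15 | 4.22 | 0.988 |
| 0.20 | 3.16 | 0.885 |
| 0.25 | 2.53 | 0.716 |

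At SD 0.20 the arm estimate would be 0.02 (95% CI 0.008 to 0.032, p = 0.0016). Each between-arm difference would be 0 ± 0.018.

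**4. Gating on the overall test.** The large-sample 2-df test rejects when χ² > 5.99. With three equal arms, the largest squared pairwise z is at least 3/4 of χ², so at least 4.49, which exceeds 1.96² = 3.84. A significant overall test therefore always comes with a significant pair, and the family-wise rate when all arms are equal is 5.0%. In simulation with one arm shifted, the false-claim rate on the remaining null pair was about 4 to 5%.

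**5. Power cost of the gate.** One arm is shifted by k standard errors of an arm mean. The figure is the chance of detecting at least one true difference.

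| k | Ungated | Gated |
|---|---|---|
| 2 | 0.43 | 0.29 |
| 3 | 0.73 | 0.58 |
| 5 | 0.98 | 0.96 |

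At k = 3, Tukey's method gives 0.57. A shift of 3 standard errors is 3/√1000 = 0.095 SD, or 0.019 logMAR at SD 0.20.

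**6. Two eyes per subject.** Protocol 8.1 includes all treated eyes. Let both eyes of a bilateral subject be in the same arm, with within-subject correlation r. The variance of an arm mean exceeds the independent-eyes value by a factor I = 1 + r if all subjects are bilateral, or I = 1 + r/1.5 if half are. An ordinary 2-df test then has error exp(−5.99/(2I)) = 0.05^(1/I).

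| r | Half bilateral | All bilateral |
|---|---|---|
| 0.3 | 8.2% | 10.0% |
| 0.5 | 10.6% | 13.6% |

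The 5% in step 4 therefore does not carry over to all treated eyes analysed as independent.

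**The case against.** The reference to baseline in 8.1 may only define a change score, and a two-sample t-test of change is by nature a between-group test. SAP 1.6 reads it that way. This stands as far as it goes: the protocol leans towards comparing arms. It still leaves three unranked pairs, and the signed-rank alternative keeps the before-after reading open.

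This is also a Phase 2 study with no stated alpha, and the SAP openly makes no multiplicity adjustment and calls its results descriptive. Its t-tests are labelled supportive and use unequal variances as a sensitivity check. That stands for the interim analysis, from which no confirmatory claim is licensed. It does not reach the protocol's 6-month primary, which carries no descriptive label and for which p-values are proposed. The SAP governs over the protocol where they conflict, but this version designates no deciding 6-month contrast.

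A reader might infer that the before-after and between-arm analyses would contradict each other. The documents do not support that. They answer different questions, and both answers in step 3 of the working can be true together. The difficulty is that the plan does not say which question is primary.

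A reader might also add UCVA and Kmax to the error count. Those endpoints are designated secondary, and this point concerns the single primary endpoint.

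Finally, a gated overall test is not the only valid choice: one named contrast or an adjusted set of pairs would also settle the matter. That is fair. The gate suits a trial that ranks none of its regimens, and it loses no power against Tukey.

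**Conclusion.** The concern holds in a limited form. Protocol 8.0 and 8.1 leave the deciding comparison for the 6-month CDVA primary unnamed, and their non-normal fallback cannot compare arms at all. If significance claims are made from unadjusted pairwise tests at two-sided 5%, the family-wise false-positive rate is 12.2%, assuming equal arms and one eye per subject. If before-after changes are used instead, a one-letter shift shared by all arms would be significant in each arm with probability 0.72 to above 0.999 over the assumed SDs. That result would say nothing about the regimens.

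These rates measure harm only if such claims are made. Alpha, allocation, SD and shift are assumptions, because the documents give none of them. The SAP cites protocol version 4.3, while the protocol reviewed is headed 04.1 with a history running to 04.2. SAP 1.6 restates the same endpoint and t-tests, so the gap probably persists, but the later text should be checked.

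**What to change.** In Protocol 8.0, 8.1 and the summary, state that:
- the primary comparison is the overall three-group (2-df) test of 6-month change in CDVA between the randomised UVA groups, at two-sided 5%;
- the three pairwise comparisons are interpreted at 5% only if the overall test is significant;
- within-group changes from baseline are descriptive;
- for non-normal data the signed-rank test is replaced by a between-group test, such as Kruskal-Wallis followed by rank-sum tests under the same gate;
- the analysis uses either one eye per subject (for example the primary eye of SAP 3.7) or a model that accounts for the correlation between a subject's two eyes.

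In SAP 1.6 and 5.1, report the overall test from the ANOVA already planned, labelled descriptive for the interim analysis.

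The cost is wording, one more line of output and, if all treated eyes are kept, a model for paired eyes. No extra subjects or visits are needed. Power for an isolated pairwise claim falls, for example from 0.73 to 0.58 at a moderate effect. That is a real loss, but about what Tukey's method would also cost, and part of the ungated figure comes from the inflated error rate. Because the study is under way and interim data are being analysed, the choice should be dated and made without reference to results by arm.

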8.2 SAMPLE SIZE JUSTIFICATION

Three thousand subjects will be enrolled in this open-label, prospective multicenter trial. One or both eyes of each patient may be enrolled and evaluated, based on whether treatment is unilateral or bilateral, based on clinical indications. All eyes treated (single or both eyes of an individual subject) will be included in the analysis of safety and efficacy.

A substantial number of eyes will need to be treated and evaluated in this study in order to obtain sufficient data to facilitate the analysis of potential differences between and among patient groups for each study indication. For example, it is expected that presenting disease severity, prior treatment (e.g. Intacs), subject age, and corneal thickness will impact the magnitude of effect of procedure efficacy for the treatment of keratoconus, forme fruste keratoconus, post-LASIK ectasia, pellucid marginal degeneration, and forme fruste pellucid marginal degeneration. Accordingly, in order to perform analyses with adequate study power, a large sample size is required.

A large sample size for a study involving fewer but similar indications is not unprecedented, as FDA clearance was previously granted for the conduct of a clinical study involving only keratoconus and post-LASIK ectasia (ref: <http://clinicaltrials.gov/ct2/show/NCT01459679>). Although that study was a Phase 3 clinical trial, it is expected that the study power needed to support analyses and conclusions of this proposed CXXLUSA study will be similar and further justifies the proposed sample size.

8.3 SAFETY

AEs, SAEs, and other findings will be summarized by presenting the percentages of subjects with each event. Continuous endpoints will be summarized using summary statistics such as means, medians, standard deviations, minima, maxima, and relevant percentiles.

9.0 RECORD RETENTION

The investigator shall maintain all subject records for a period of two years after the investigation is discontinued and FDA is notified.

The investigator must maintain accurate records of the receipt of all investigational material shipped by the sponsor, including the date and lot numbers received. In addition, accurate records must be kept on the amount and date that the investigational material, by lot number, was used and for each subject.

The investigator must assure that study supplies are used only in conjunction with subjects enrolled in the study and under the direct supervision of the investigator or co-investigators.

10.0 STUDY MONITORING REQUIREMENTS

CXLUSA, LLC, or designee, will monitor this study. Study monitoring involves the following elements:

CXLUSA personnel, or designee, may meet in person or via teleconference with investigators prior to the initiation of the study in order to review the adequacy of the subject population, facilities, and equipment with respect to the needs of the study, and to familiarize the investigator and support staff with the study protocol.

CXLUSA personnel, or designee, may meet in person or via teleconference with the investigators at the time enrollment is initiated in order to ensure that subjects are being properly selected, that the methods described in the study protocol are thoroughly understood by the investigator, and that study data are being correctly recorded.

CXLUSA personnel, or designee, may visit in person or communicate via teleconference with the clinical site at any time during the course of the study to review and/or collect completed case report forms. Additionally, telephone consultation will occur as necessary during the course of the study to ensure the proper progress and documentation of the study findings.

11.0 PROTOCOL DEVIATIONS/AMENDMENTS

An investigator may deviate from the protocol to protect the life or physical well-being of a subject in an emergency, and must notify the sponsor and the reviewing IRB within 5 working days after the emergency occurred. Except in such an emergency, an investigator may not deviate from the protocol unless he/she obtains the prior approval of CXLUSA. FDA and IRB/EC approval is also required in accordance with 812.35(a).

04	14 October, 2016	Additional exclusion criteria added (nystagmus or any condition investigator believes would prevent steady gaze during treatment, inability to cooperate with diagnostic tests, enrollment in another ophthalmic trial); changed last required study visit from 8 months to 6 months post-op; changed mandatory assessment from 4 months to 3 months post-op; secondary endpoints changed from UCVA, K _{max} , and manifest refraction spherical equivalent (MRSE) to UCVA and K _{max} ; deleted DSMB assessment after 250 subjects treated; CDVA to be assessed by masked evaluator; clarified that all eyes treated (single or both eyes of individual subject) will be included in analysis of safety and efficacy; clarified Sect. 4.1 that epithelium is not to be removed; other minor changes.
04.1	27 October, 2016	Deleted “Official Correspondent: [name], JD” from cover page to avoid confusion as to parties to contact; clarified study population age in 1.0 Protocol Summary from > 8 years old to >= 8 years old; Sect. 4.1, corrected information related to same-day treatment options from “3 options” to “2 options”.
04.2	14 November, 2016	In response to IRB comments, changed exclusion criteria of “Active herpes simplex corneal disease” to “Any history of herpes simplex corneal disease in an eye to be treated” and changed post-op topical anesthetic from “Tetracaine 0.5% to 0.05% PRN eye pain for up to 3 days” to “Proparacaine 0.5% every 6 hours as needed for up to 24 hours post-procedure”.

APPENDIX 1: FLIP CHART OF RIBOFLAVIN CORNEAL LOADING

**Riboflavin Corneal Loading
CXL-05 Study Flip Chart
11.10.15 Draft**

**All Study Investigators Must
Review this Entire Presentation
Prior to Participating
in the Study**

[figure not shown]
**Introduction:
Flip Chart Precedents
Botany, Medicine, Ophthalmology**

Leaf Color Chart

Irrigated Rice Research Consortium (IRRC)
in collaboration with the University of California Cooperative Extension

Diabetic Retinopathy Study

[figure not shown]
Copyright © 2001 Fundus Photograph Reading Center
Department of Ophthalmology and Visual Sciences University
University of Wisconsin

Three Key Aspects to Corneal Riboflavin Loading

[figure not shown]
- 1. Homogeneity**
(Is the loading even or uneven/patchy?)
- 2. Concentration**
(How much riboflavin green color is present?)
- 3. Location**
(Where in the cornea is the riboflavin?)

Slit Lamp Examination Must be Performed after Riboflavin Loading of the Cornea and Prior to UVA Application to Confirm Adequate Corneal Riboflavin Loading. Riboflavin Has a Distinct Green Appearance on SL Examination.

**White and Cobalt Blue
are Both Helpful in Slit Lamp
Assessment of Corneal Loading**

[figure not shown]
**White Slit
Lamp Beam**

**Cobalt Blue
Slit Lamp Beam**

[figure not shown]
1. Homogeneity
**Objective: Homogeneous
(Not Patchy) Loading**

Stromal Loading Must Be Homogeneous Prior to UVA Application

[figure not shown]

This is not
homogeneous loading.
Note more riboflavin
at superior arrow
than inferior arrow.

**Again, Patchy
Non-Homogeneous Loading**

[figure not shown]

**Another Example of
Non-Homogeneous Loading**

[figure not shown]

**Note more riboflavin
At inferior arrow
than superior arrow.**

Homogeneous, Well Distributed Riboflavin Loading (White Light)

[figure not shown]
Homogeneous, Well Distributed Riboflavin Loading (Blue Light)

[figure not shown]
2. Concentration

**Objective: Grades III-V/V
Prior to UVA Application.
Riboflavin acts as a catalyst
so Grade V/V is not more
effective than Grade III.**

[figure not shown]
**Before Riboflavin Application
Grade 0/V -No Green Visible**

[figure not shown]
**Grade I/V-Not Adequate for UVA Tx
Mild Green Tint Just Visible**

[figure not shown]
**Grade II/IV -Not Yet Adequate for UVA
Substantial Green Visible**

[figure not shown]
**Grade III/V – Adequate for UVA
Obvious Green Color**

Grade IV/V Adequate for UVA Bright Green Appearance

[figure not shown]
**Grade V/V- Adequate for UVA
Strong Bright Green Color**

[figure not shown]
3. Location

**Objective: Well Loaded Corneal
Stroma and Minimal Loading of
Epithelium to Optimize UVA
Penetration into Corneal Stroma.**

**Anterior Chamber Flare is NOT Required
or Desirable Before UVA Application
Goal is to Cross-Link Cornea, not AC**

[figure not shown]
Superficial Green Color Only In Tear Film

Green in Surface
Tear Film Only

No Green in
Corneal Stroma

[figure not shown]
Well Loaded Stroma

Corneal
Stroma is
Well Loaded

[figure not shown]
Epithelium Shows
Only Minimal Green
(Opposite of Surface
Stain Only)

Artificial Tears

[figure not shown]

**After SL Confirmation
of Adequate Stromal
Riboflavin Loading,
Applying Artificial Tears
for ~30 Sec Allows the
Epithelium to Clear Prior
to UVA Application**

Excellent Stromal Loading and Minimal (No Visible) Epithelial Loading

End of Presentation

